- p. For practical reasons, the timing of DXA may vary from the actual time of the visit, depending on the DXA availability (DXA appointment). The screening visit (days -35 to -1 [visit 1]) DXA can be performed once the subject has been deemed eligible based on screening laboratory tests, or at visit 2 but must be performed before randomization. The week 52 (visit 15) DXA should be performed between week 50 and week 52, inclusive. For subjects who are withdrawn from the study prior to completion, a DXA will be completed as soon as possible after study drug discontinuation (preferably within 2 weeks).
- q. For HBsAG, anti-HCV antibodies, anti-HBs antibodies, anti-HBc antibodies and anti-HIV antibodies.
- r. Pharmacodynamic samples will be taken predose (1 hour) at day 1 (visit 2), week 4 (visit 3), week 12 (visit 5), week 24 (visit 8), at week 52 (visit 15) and week 55 (visit 16). Markers include LH, FSH, E2, SHBG, androstenedione, dehydroepiandrosterone, estrone and testosterone.
- s. Pharmacokinetic samples to be taken predose at week 4 (visit 3), week 12 (visit 5), week 24 (visit 8), and at EOT/ED week 52 (visit 15) and at 1 to 3 hour postdose at week 4 (visit 3). A predose sample will be collected for any subject with a signal of elevated ($> 3 \times$ ULN) transaminases. For the week 52 (visit 15) PK/PD samples, the last dose of study drug should be administered the day prior to the week 52 (visit 15) visit. Sites should collect week 52 (visit 15) PK/PD samples approximately at the same time when study drug would typically be given on site.
- t. A clinician will administer the C-SSRS measure electronically at the clinic visit, prior to any invasive procedures. This will be administered electronically via the site tablet at screening, (visit 1), week 0 (visit 2), week 12 (visit 5), week 24 (visit 8), EOT/ED week 52 (visit 15) and the follow-up visit (week 55 [visit 16]).
- u. ePRO assessments are self-administered electronically via the site tablet at the study site at week 0 (visit 2), week 4 (visit 3), week 12 (visit 5), week 24 (visit 8) and week 52 (visit 15). The ePRO assessments are administered before any other study assessments/procedures are performed; assessments at visit 2 must occur prior to randomization/first dosing; assessments at week 4 (visit 3), week 12 (visit 5), week 24 (visit 8) must occur prior to dosing; in the event a subject withdraws from the study, efforts to collect information on the site-based subject-reported outcome measures should be made before or shortly after discontinuation.
- v. Subjects will be assigned study drug as a kit containing either fezolinetant or placebo. Study drug intake will be done with a glass of room temperature tap water. The first intake of study drug will take place at the study site on day 1 (visit 2) under the supervision of the study staff. On study visit days (except for EOT/ED week 52 [visit 15]), the daily dose of study drug will be taken at the study site, under the supervision of the study staff, after collection of predose blood samples. On all other days throughout the treatment period, subjects will be instructed to take their study drug at home, in the morning with water.
- w. Subjects will be asked to return all unused study drug. Compliance of study drug intake will be assessed by counting returned study drug and recorded in the source documents and the IRT.
- x. AEs and intake of concomitant medication(s) will be monitored continuously from informed consent until the last study-related activity.
- y. Screening (visit 1), Randomization, week 0 (visit 2) and EOT/ED week 52 (visit 15) visits, must be conducted in the clinic and not home healthcare, telemedicine conferences or a local laboratory.

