Descriptive statistics on the actual values will be summarized by visit and treatment arm. Pharmacokinetics may be evaluated by a population pharmacokinetic approach. All details of population analyses will be described in a separate analysis plan and a separate report will be written. When deemed necessary, data from this study may be combined with data from other studies.

Pharmacodynamics:

[figure not shown]
Individual plasma hormone concentration values and actual sampling times relative to study drug intake will be listed. Descriptive statistics on the actual values and changes from baseline values will be summarized by assessment timepoint and by treatment arm. Pharmacodynamic data and efficacy data may be evaluated by a population pharmacodynamics or population pharmacokinetic/pharmacodynamic approach. All details of population analyses will be described in a separate analysis plan and a separate report will be written. When deemed necessary, data from this study may be combined with data from other studies.

Interim analyses:

Not applicable.

V. FLOW CHART AND SCHEDULE OF ASSESSMENTS

Flow Chart:

* An extra 15 screening days are allowed for repeat biopsy, if necessary (days -50 to -1, including the screening visit [visit 1] assessments).

Table 1 Schedule of Assessments

Assessments	Screening Visit ^{a,x}	Randomization ^x	Treatment Period									Follow-Up Visit ^b
	Study Visit	Visit 1	Visit 2	Visit 2b	Visit 3	Visit 4	Visit 5	Visit 6	Visit 7	Visit 8	Visits 9, 10, 11, 12, 13 and 14	Visit 15/ EOT/ED ^y
Time of Visit	Week -5 to -1	Week 0	Week 2	Week 4	Week 8	Week 12	Week 16	Week 20	Week 24	Weeks 28, 32, 36, 40, 44 and 48	Week 52	Week 55
Visit days	Days -35 to -1	Day 1	Day 15	Day 29	Day 57	Day 85	Day 113	Day 141	Day 169	Day 197, 225, 253, 281, 309 and 337	Day 365	Day 386
Visit Window (days) ^c	-35 to -1	-	± 3	± 3	± 3	± 3	± 3	± 3	± 3	± 3	-14 /+ 6	± 3
Informed consent ^d	X											
Inclusion/exclusion criteria	X	X										
Medical history/ concomitant diseases	X											
Mammogram ^e	X										X	
Demographic data ^f	X											
Physical examination ^g	X	X ^h		X ^h	X ^h	X ^h	X ^h	X ^h	X ^h	X ^h	X	X
Urine pregnancy test	X											
Clinical laboratory ⁱ and urinalysis	X	X	X ⁱ	X	X	X	X	X	X	X	X	X
Vital signs ^j	X	X		X	X	X	X	X	X	X	X	X
12-lead ECG ^k	X										X	
Pap test ^l	X											
Transvaginal ultrasound (TVU) ^m	X										X	
Endometrial biopsy ⁿ	X ⁿ										X ^o	
DXA ^p	X										X	
Serology ^q	X											

Table continued on next page

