1.3.2 Summary of Clinical Studies

To date, 10 clinical studies have been completed with fezolinetant; 6 phase 1 studies (ESN364-CPK-101, ESN364-CPK-102, ESN364-CPK-103, 2693-CL-0020, 2693-CL-0006 and 2693-CL-009) and 4 phase 2 studies (ESN364-HF-204, ESN364-UF-02, ESN364-PCO-201 and ESN364_HF_205). Two of the 4 phase 2 studies were performed in women with MR-VMS (Studies ESN364_HF_204 and ESN364_HF_205). The 10 completed studies with fezolinetant are shown in [Table 2](#).

The pharmacokinetics of fezolinetant were characterized in studies in healthy subjects and in patients with VMS. After oral intake, fezolinetant showed generally dose proportional pharmacokinetics at doses between 20 and 60 mg once daily in female subjects. Maximum concentration (C_{max}) was generally reached within 1 to 4 hours postdose with terminal half-life ranging between 4-6 hours in healthy subjects and patients. With a once daily dose regimen, steady state plasma concentrations were achieved by approximately day 2 with minimal accumulation. Low plasma protein binding of fezolinetant (50%) was observed with almost equal distribution of fezolinetant into red blood cells and plasma, with a blood-to-plasma ratio of 0.9.

Fezolinetant undergoes extensive metabolism, primarily by cytochrome P450 (CYP) 1A2 enzyme, to form the major metabolite ES259564. A strong CYP1A2 inhibitor (fluvoxamine) increased fezolinetant area under the concentration-time curve (AUC) and C_{max} approximately 9-fold and 1.8-fold, respectively, while smoking was shown to decrease AUC and C_{max} to a geometric least squares mean ratio of 48.3% and 71.7%, respectively (2693-CL-0006).

In a recently completed mass balance study (ESN364_CPK_103), the routes of excretion of fezolinetant were found to be via urine (76.9%) and feces (14.7%). In urine, a mean of 1.1% of the administered fezolinetant dose was excreted unchanged and 61.7% of the administered dose was excreted as metabolite ES259564.

Fezolinetant did not show clinically significant food effects on its pharmacokinetic exposure parameters (ESN364_CPK_101). Based on population pharmacokinetic modeling analyses, body weight was not identified as an important predictor of AUC. However, male subjects are predicted to have 53.2% reduction AUC and 14.9% reduction in C_{max} , compared to females. Asian population was predicted to have a 25% increase in steady-state C_{max} and AUC, which is consistent with clinical observations (Study 2693-CL-0020)

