5.9 Test Drug Concentration

Blood samples for pharmacokinetics of fezolinetant and metabolite ES259564 will be collected from every subject. Pharmacokinetic samples will be taken predose at week 4 (visit 3), week 12 (visit 5), week 24 (visit 8), week 52 (visit 15), as well as any subject with a signal of elevated ($> 3 \times \text{ULN}$) aminotransferases [[Appendix 12.4 List of Excluded](#)]

[Concomitant Medications](#)]. Pharmacokinetic samples will be taken 1 to 3 hours postdose at week 4 (visit 3).

Details on sampling, processing, storage and shipment procedures will be provided in a separate central laboratory manual.

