7.7 Analysis of Pharmacokinetics

Descriptive statistics (e.g., n, mean, SD, minimum, median, maximum, coefficient of variation [CV], geometric mean and geometric CV) on the actual values will be summarized for plasma concentrations of fezolinetant and the major metabolite ES259564 by visit and treatment arm. Pharmacokinetics may be evaluated by a population pharmacokinetic approach. All details of population analyses will be described in a separate analysis plan and a separate report will be written. When deemed necessary, data from this study may be combined with data from other studies.

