6.10 Additional Conventions

6.10.1 Analysis Windows

Study Day for analysis windows will be calculated as date of visit/assessment – first dose date +1.

Study Day for the follow-up (FUD) phase will be calculated as date of visit/assessment – last dose date of study treatment (Date of EOT).

Except for adverse events, for the analysis window (weeks prior to the follow-up period), the last day is always 1 day after the last day of exposure to double-blind treatment.

The end of overall treatment is defined as the last day of treatment +1 and the follow-up period begins at last overall treatment + 2 days and onward (Follow-up Study Day 2).

The data summary by visits will be done following the analysis windows specified in the table below:

Analysis	Scheduled	Analysis Windows (day)				
Visits	Day in Protocol	a)	b)	c)	d)	e)
Baseline	Day 1	Last non-missin	ng value on or prio	or to day 1 (inclu	sive)	
Week 2	Day 15	2 to 22				
Week 4	Day 29	23 to 43	2 to 43	2 to 57		
Week 8	Day 57	44 to 71	44 to 71			
Week 12	Day 85	72 to 99	72 to 99	58 to 127	2 to 127	
Week 16	Day 113	100 to 127	100 to 127			
Week 20	Day 141	128 to 155	128 to 155			
Week 24	Day 169	156 to 183	156 to 183	128 to 267	128 to 267	
Week 28	Day 197	184 to 211	184 to 211			
Week 32	Day 225	212 to 239	212 to 239			
Week 36	Day 253	240 to 267	240 to 267			
Week 40	Day 281	268 to 295	268 to 295			
Week 44	Day 309	296 to 323	296 to 323			
Week 48	Day 337	324 to 351	324 to 351			
Week 52	Day 365	352 to 376	352 to 376	268 to 376	268 to 376	2 to 376
Follow-up	Day 386	Last treatment + 2 days and onwards				

a) Apply to Clinical laboratory and urinalysis

b) Apply to Vital signs

- c) Apply to Blood PD/PK sample, EQ-5D-5L, MENQoL
- d) Apply to C-SSRS
- e) Apply to 12-lead ECG

For TVU and DXA, the week 52 analysis window is day 2 to last treatment + 30 days. For endometrial biopsy, refer to Section 6.5.5 for analysis window.

As a general rule, if more than one observation exists within the analysis window, the observation closest to the scheduled visit day will be selected for that visit. If there are two observations that have the same distance from the scheduled day, the value that is after the scheduled day will be selected in the analysis. If more than one observation is made on the same day, an average value if continuous or the worst value if categorical will be included in the analysis.

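### SAP 6.10.1 does not exempt PK samples from same-day averaging, so a by-visit concentration summary run under it would merge the Week 4 predose and 1 to 3 h postdose values

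*Protocol*

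**What the plan says.** **Sampling.** Footnote s to Table 1 of the protocol reads "Pharmacokinetic samples to be taken predose at week 4 (visit 3), week 12 (visit 5), week 24 (visit 8"), and continues "and at EOT/ED week 52 (visit 15) and at 1 to 3 hour postdose at week 4 (visit 3"). Protocol 5.9 repeats the extra sample: "Pharmacokinetic samples will be taken 1 to 3 hours postdose at week 4 (visit 3"). Protocol 5.7.3 gives the same scheme. Footnote v has the visit-day dose taken on site after the predose blood draw, so the two Week 4 samples fall on the same calendar day. At Week 52 the last dose is taken the day before and the sample is drawn at about the usual dosing time, so it is a trough of roughly 24 h.

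**Summary rule in the SAP.** SAP 6.10.1 sets the windows for by-visit data summaries. Column c of the window table carries the note "Apply to Blood PD/PK sample, EQ-5D-5L, MENQoL". The rule for several values on one day is "If more than one observation is made on the same day, an average value if continuous". No exception by nominal PK time is stated.

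**Whether concentrations are summarised.** The synopsis says "Descriptive statistics on the actual values will be summarized by visit and treatment arm". Protocol 7.7 says that descriptive statistics will be "summarized for plasma concentrations of fezolinetant and the major metabolite ES259564 by visit and treatment arm". SAP 5.3 and 6.5 name plasma concentration at Weeks 4, 12, 24 and 52 as an exploratory variable, and SAP 6.5 says that safety parameters in general receive summary statistics. SAP 6.6, however, commits only to listing the concentrations and places PK methods in a separate plan.

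**The concern.** A trough and a sample taken 1 to 3 h after dosing measure different things. With a short half-life and once-daily dosing they differ many-fold. Averaging them at one week and reporting a pure trough at the other three puts unlike quantities in the same row of a table. A reader would see exposure drop sharply between Week 4 and Week 12 and might suspect declining adherence, enzyme induction or a supply problem. None of these would be needed to explain it, because the averaging rule alone produces the drop.

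The SAP already has the right idea elsewhere: SAP 6.7 summarises hormones by visit and time point, although hormones are sampled once per visit. The concentrations are the data that need that level, and they do not have it.

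**Working it through.** The plan states no figure for this point, so there is none to reproduce. The check asks how far the Week 4 average would lie from the trough at the other weeks if exposure did not change.

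**Inputs (Protocol 1.3.2).** For half-life *T* the protocol gives a "terminal half-life ranging between 4-6 hours". Peak concentration is generally reached 1 to 4 h after dosing, and steady state is reached by about day 2 with minimal accumulation. The dosing interval is 24 h. The postdose sample is taken at *t* = 1 to 3 h.

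**Consistency of the inputs.** Accumulation = 1/(1 − 2^(−24/*T*)). For *T* = 4, 5 and 6 h this gives 1.02, 1.04 and 1.07, which agrees with minimal accumulation.

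**Model A: first-order decline from the postdose sample to 24 h.** Trough/postdose = 2^(−(24−*t*)/*T*). Average/trough = (1 + postdose/trough)/2.

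| *T* (h) | *t* (h) | Trough/postdose | Postdose/trough | Average/trough |
|---|---|---|---|---|
| 4 | 1 | 0.0186 | 53.8 | 27.4 |
| 4 | 3 | 0.0263 | 38.1 | 19.5 |
| 6 | 1 | 0.0702 | 14.3 | 7.6 |
| 6 | 3 | 0.0884 | 11.3 | 6.2 |

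Model A ignores absorption. If the peak comes as late as 4 h, a sample at 1 h is still on the rising part of the curve, and Model A overstates the ratio.

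**Model B: one compartment, first-order absorption, steady state.** C(*t*) is proportional to e^(−k_e·*t*)/(1 − e^(−24·k_e)) − e^(−k_a·*t*)/(1 − e^(−24·k_a)), with k_e = ln 2/*T* and k_a solved from Tmax = ln(k_a/k_e)/(k_a − k_e). The grid was *T* = 4, 5, 6 h; Tmax = 1, 1.5, 2, 3, 4 h; *t* = 1, 2, 3 h (45 combinations).

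- Lowest ratio (*T* = 6, Tmax = 4, *t* = 1): postdose/trough 4.8, average/trough 2.9.
- Highest ratio (*T* = 4, Tmax = 1, *t* = 1): postdose/trough 50.8, average/trough 25.9.
- Central example (*T* = 5, Tmax = 2, *t* = 2): postdose/trough 18.8, average/trough 9.9.
- Median average/trough over the grid: 7.8.

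**Result.** Across both models the average is about 3 to 27 times the trough. The apparent fall from Week 4 to Week 12 would be 1 − 1/2.9 = 66% (rounded) at the small end and 1 − 1/27.4 = 96% at the large end, with exposure unchanged. If the two Week 4 samples are kept apart, the expected ratio of the Week 4 predose value to the later troughs at steady state is about 1.

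**The case against.** The strongest reply is that the SAP's own PK section plans no such table. SAP 6.6 lists concentrations, and a listing averages nothing. It sends PK methods to a plan that is not among these documents. SAP 6.5 says that the later sections set the method, so its general sentence about summary statistics should not override 6.6. The averaging paragraph in SAP 6.10.1 opens as a general rule. Protocol 7.7 does not say that each subject contributes one value per visit, and separate predose and postdose rows under Week 4 would also be a summary by visit.

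Much of this stands: the averaged value is a possible output, not a certain one. It does not remove the problem. The window table governs by-visit summaries, so naming PK samples in column c has no purpose if they are only listed. Protocol 7.7 reserves the separate plan for population analyses and makes the descriptive summary a commitment of its own. Either the summary is produced and the written rule spoils Week 4, or it is not produced and Protocol 7.7 is not carried out by the SAP. Each case calls for an edit.

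Two stronger readings should be resisted. A reader might infer that the trial's only scheduled postdose concentration would be lost. It would not: concentrations are listed individually, Protocol 5.7.3 requires exact sampling and dosing times, and a population PK analysis can use them. A reader might also infer that the assessment of exposure and transaminase elevations is compromised. The documents do not support this. The earlier assessment in Protocol 2.2.2 used individual predicted exposures, separate samples are drawn from subjects with transaminases above 3 × ULN, and nothing routes a Week 4 mean into a liver analysis.

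**Conclusion.** The point holds in conditional form and is minor. SAP 6.10.1, read as written, averages the two Week 4 samples. If the by-visit summary in the synopsis and Protocol 7.7 follows it, Week 4 will stand at about 3 to 27 times the trough shown at Weeks 12, 24 and 52, and the table will display a false fall in exposure. The range rests on the protocol's half-life and time to peak, and on two assumed models. It applies to the parent drug; the documents give no half-life for the metabolite, so its ratio was not computed. No combination tried made the averaged Week 4 value comparable with a trough.

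The protocol and SAP also disagree on whether a concentration summary is produced at all. The effect is confined to a descriptive exploratory endpoint. Listings and population PK need not be affected. The primary safety endpoints and the sample size are untouched.

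**What to change.** - **SAP 6.10.1:** state that PK concentrations are exempt from same-day averaging and that Week 4 predose and Week 4 1 to 3 h postdose are separate nominal time points. Only the predose value should then appear alongside Weeks 12, 24 and 52.
- **Synopsis and Protocol 7.7:** change the level of summary from visit to visit and nominal time, by treatment arm.
- **Protocol 7.7 and SAP 6.6:** decide whether concentrations are summarised or only listed, and make the two agree. If they are only listed, remove PK from column c of the window table.

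The cost is about one sentence in the SAP, matching wording in the protocol, and one extra row in the PK table if it is produced. No new data or assessments are needed.

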1 INTRODUCTION

1.1 Introduction to Fezolinetant

Fezolinetant is a small-molecule, selective neurokinin-3 receptor (NK3R) antagonist currently being developed as an innovative non-hormonal treatment specifically targeting the cause of vasomotor symptoms (VMS) in postmenopausal women (menopause-related vasomotor symptoms [MR-VMS]).

For more information, refer to the Investigator's Brochure (IB) for fezolinetant.

1.2 Background

1.2.1 Vasomotor Symptoms (Hot Flashes): Epidemiology and Etiology

VMS, commonly known as hot flashes (HFs), are the most common complaint among women entering menopause and for many women, may continue to occur for up to 5 years (although around 20% of women will continue to experience them for up to 15 years) [Stearns et al, 2003; Rossouw et al, 2002; Kronenberg, 1994]. The large prospective cohort Study of Women's Health Across the Nation found that overall prevalence of VMS was approximately 70% [Thurston & Joffe, 2011].

VMS can have a significant negative impact on quality of life and are therefore a major reason for menopausal women to seek medical attention. Despite the vast numbers of individuals affected, the physiology of VMS is not fully understood, although a disturbance in normal thermoregulatory function is thought to be the main underlying cause. The primary presentation of VMS is a subjective and transient sensation of heat, flushing and sweating that usually last 4 to 10 min and may be followed by a feeling of being chilled. VMS may be accompanied by palpitations, feelings of anxiety and sleep disruption leading to fatigue or irritability; in rare occurrence, panic may occur [Kronenberg et al, 1994; Kronenberg et al, 1990].

The most effective and commonly used treatment for VMS is hormone replacement therapy (HRT), but a Women's Health Initiative study raised questions about the long-term safety of this treatment [Rossouw et al, 2002]. Thus, current guidelines recommend a limited duration of HRT due to associated risks of breast cancer (BC), coronary artery disease, stroke and thromboembolism [de Villiers et al, 2016; Rossouw et al, 2002]. Furthermore, the current safety data do not support the use of HRT in several groups of patients (e.g., those with BC/endometrial cancer, liver disease). The perceived limitations of HRT, coupled with the limited efficacy and adverse effects observed with nonhormonal therapies (e.g., selective serotonin reuptake inhibitors) have led clinicians to search for other treatment options for VMS. One selective serotonin reuptake inhibitor is approved in the US for the treatment of MR-VMS (Brisdelle[®], low dose paroxetine). Studies of venlafaxine and fluoxetine in women with a prior history of BC have suggested that certain antidepressants with the ability to inhibit serotonin reuptake may significantly reduce MR-VMS [Loprinzi et al, 2002; Loprinzi et al, 2000; Stearns et al, 2000].

Over the past 20 years, a growing body of evidence has implicated neurokinin B (NKB) NK3R signaling in the etiology of menopausal VMS. Recent advances in the field have

demonstrated that the gonadotropin-releasing hormone (GnRH) pulse frequency is modulated by the kisspeptin/neurokinin B/dynorphin (KNDy) neurons (also known as ‘KiSS Neuron’) in the arcuate nucleus of the hypothalamus [Millar & Newton, 2013]. Neuroanatomical studies have shown that these neurons are sensitive to NKB/NK3R signaling [Hrabovszky, 2014]. By studying brain specimens at post mortem, [Rance & Young, 1991] initially showed that in postmenopausal women, hypothalamic neurons are hypertrophied and have increased NKB gene expression and neuronal activity compared with premenopausal women. This was also found to be true in ovariectomized monkeys but moreover, this change could be reversed by treatment with sex steroid replacement thus suggesting this was a dynamic change in response to reduced circulating concentrations of estradiol (E2) as occurs in the menopause [Rance, 2009]. Subsequent work in rats highlighted the importance of the hypothalamic median pre-optic nucleus in the propagation of the NKB-mediated signal that results in VMS [Rance et al, 2013]. The median pre-optic nucleus is a neural area that receives input from, and projects to, the autonomic thermoregulatory pathway, expresses NK3R and hence results in activation of heat dissipation effectors that characterize VMS. Importantly, estrogen also acts directly on the estrogen receptor alpha expressed on KNDy neurons to decrease similarly KNDy neuron activity [Ruka et al, 2016; Lehman et al, 2010]. Additionally, Crandall et al. recently found that genetic variation in tachykinin receptor 3, which is the gene that encodes NK3R, may account for the variability in experience of VMS reported among women [Crandall et al, 2017].

